## **Health care costs**

### Primary:

We hypothesize >50% average total cost reduction (charges and amount paid, examined separately), for the period from discharge through eight weeks postpartum, for the intervention versus usual care arm, irrespective of insurance status.

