### **Background, Rationale, and Context**

Despite advances in perinatal care in the U.S., maternal mortality has more than doubled over the past two decades, with substantial racial and socioeconomic disparities observed.[1] Hypertensive disorders of pregnancy (HDP) are a leading cause of perinatal morbidity and mortality, with up to 20% of maternal deaths attributed to preeclampsia.[2] In the traditional postpartum care model, many women are not seen for follow-up until six weeks postpartum, with the highest risk women typically scheduled for follow-up three to seven days after discharge. Thus, the postpartum period is a time of particular susceptibility for maternal morbidity and mortality resulting from undiagnosed or inadequately managed HDP.[3] Women from lower socioeconomic status (SES) groups, as well as racial and ethnic minority groups, disproportionately experience an increased risk for adverse consequences from HDP.[4] To mitigate this risk, the American College of Obstetrics and Gynecology (ACOG) recommends blood pressure monitoring (BPM) at 72 hours and through 7-10 days postpartum for women with HDP.[5]

Postpartum readmission for HDP is not limited to antenatally diagnosed HDP; women at “low-risk” account for a significant proportion of readmissions for HDP.[6] ACOG guidelines for postpartum care in lower-risk women recommend an initial postpartum visit by three weeks and a final comprehensive visit by 12 weeks postpartum.[7] However, the majority of readmissions for postpartum HDP occur prior to three weeks, suggesting that this care model is likely inadequate for many women and may contribute to missed or delayed diagnosis and treatment of HDP. In our own, highly diverse patient population, with nearly two-thirds of pregnancies covered by Medicaid or without insurance, compliance with recommended in-person, postpartum visits through this period, among women with higher and lower risk, is less than 50% (internal data).

Given the postpartum risks, women with known HDP experience increased length of stay during their initial postpartum admission.[8] While the increased length of stay has been associated with decreased readmission for HDP, it has also been associated with a significant increase in delivery hospitalization charges.[8] Remote BPM in the postpartum period has been proposed as an intervention to achieve increased monitoring without extending inpatient length of stay.[9]

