### **Primary Objective**

Evaluating remote BP monitoring (rBPM) in a highly diverse patient population for:

- Feasibility and acceptability (patient adherence and satisfaction)
- Increased adherence to ACOG guidelines particularly to evaluate the impact of rBPM on the proportion of women with antepartum/delivery hypertensive disorder with blood pressure measures obtained within 72 hours and seven days of discharge and for all women within three weeks postpartum
- Reduced delivery admission length of stay (LOS)
- Reduced utilization of emergency/acute care services (Emergency Department, OB Triage, Urgent Care)
- Reduced incidence of readmission and readmission LOS
- Assess impact of a rBPM intervention on total health care costs to the patient during the first eight weeks postpartum.

Comparisons:

- rBPM relative to usual standard of care (SOC)
- Performance within racial and socioeconomic subgroups

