#### **If BP critically elevated ( $\geq 160/110$ )**

- Alert is generated through the BabyScripts app for either diastolic alone or systolic alone readings or if both readings are above the threshold

- Subject receives an immediate text and email message via BabyScripts letting subject know they have a critically elevated BP reading and asking the subject to complete a symptom checklist directly in the app. If they have no symptoms, the “no symptoms” icon must be checked in the app.
- On-call MFM staff is alerted by BabyScripts call center within 60 minutes [14-19].
- Provider (or nurse – see 2nd bullet below) calls subject for further evaluation and instructions within 45 minutes:
  - If this is new onset hypertension irrespective of symptoms, the subject is referred to OB triage and instructed to present without delay.
  - If subject also has a chronic or known history of high BP, but no other symptoms, then a RN reviews the BP measurements, discusses with the clinic or on-call MFM physician, and contacts the subject with the provider’s recommended instructions.

For the subjects in the rBPM study arm, acceptability and user experience data will be collected via on-line REDCap questionnaire ~ 21 – 28 days after study enrollment, or within one week of the subject’s completion of the study. A unique link to the REDCap questionnaire will be sent via email to the subject. If the questionnaire is not completed within 1 week of being sent, a reminder email to complete the survey will be sent weekly for a maximum of 3 weeks. Completion of this on-line survey is expected to take <= 5 minutes.

Per standard of care, the rBPM study arm subject’s initial postpartum OB provider visit will be scheduled either at ~1 week after delivery for high risk subjects and at ~4-6 weeks after delivery for subjects with a low risk of postpartum complications. Additional follow-up medical care visits may be scheduled at the discretion of the provider and the subject. All follow-up medical care, regardless of the study arm, will be at the expense of the individual subject.

The subjects randomized to the experimental study arm will be provided with a specialized BP cuff/monitor at no cost. The subject will be able to keep the BP cuff/monitor for personal use after they have completed the study. The subject does not need to return the monitor.

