### Secondary:

Remote BPM will decrease the duration of stay in the postpartum unit, with women with remote BPM discharged earlier than those with usual care, with a median, absolute decrease of length of stay of >1 day(s), irrespective of insurance status.

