## **Analytical Plan**

The subject will complete a baseline demographic questionnaire at the time of enrollment. This questionnaire will be completed electronically through a unique link via REDCap. Additionally, subjects in the rBPM study arm will be asked to complete a post-study questionnaire electronically through a unique link via REDCap ~ 1 week after subject has completed the study.

The following EHR-based clinical measures will be obtained from each subject:

- Demographics
- History of hypertension or use of blood pressure lowering agents
- Pregnancy-related data (e.g. blood pressure, pre-pregnancy BMI, weight gain, complications, pre-pregnancy diabetes, gestational diabetes, delivery complications)
- Birth outcomes, including gestational age at delivery, cesarean or vaginal delivery, singleton or multiparous delivery, birth weight
- Length of stay of admission and any readmissions through 12 weeks postpartum
- Use of blood pressure lowering agents through 12 weeks postpartum

We will link EHR, BP, baseline demographic questionnaire data, billing, and user satisfaction data to inform study questions as described above. Data will be reviewed for missingness, with multiple imputation performed as appropriate. Initially, data will be analyzed using descriptive statistics. Comparison between groups may be performed using chi square tests for proportions, and t-tests or ANOVA procedures for continuous variables. Crude and adjusted regression analysis will be performed to identify independent outcome predictors. Other inferential statistical analysis will be conducted as appropriate.

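### The primary cost outcome starts at discharge although the objective covers the first eight weeks postpartum, and no median-based analysis is named for the length-of-stay hypotheses

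*Combined protocol and SAP*

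**What the plan says.** All references are to the combined protocol and SAP.

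- **Cost, as an objective.** The Primary Objective section has "Assess impact of a rBPM intervention on total health care costs to the patient during the first eight weeks postpartum". The Outcome Measures list repeats this in nearly the same words. Neither mentions discharge as the start.
- **Cost, as a hypothesis.** Under Health care costs, Primary, the plan states "We hypothesize >50% average total cost reduction (charges and amount paid, examined separately), for the period from discharge through eight weeks postpartum". The window therefore opens at discharge.
- **Why the delivery stay matters.** The Background says of longer inpatient stay in women with known hypertensive disorders that "it has also been associated with a significant increase in delivery hospitalization charges". The Outcome Measures section expects providers to discharge earlier when they know blood pressure will be checked at home.
- **Length of stay.** The first Secondary entry under Clinical outcomes expects earlier discharge "with a median, absolute decrease of length of stay of >1 day(s), irrespective of insurance status". The next Secondary entry expects a shorter median stay for readmissions.
- **Analysis.** The Analytical Plan says group comparisons may use chi-square tests for proportions and "t-tests or ANOVA procedures for continuous variables". It adds regression and a general allowance for other methods. It names no rank, quantile or other median-based method. Billing data are to be linked to the other sources.
- **Programme resources.** "The subjects randomized to the experimental study arm will be provided with a specialized BP cuff/monitor at no cost". The app is also free to the subject, and coordinator training, a call centre and round-the-clock clinical response are described. No section plans to collect these costs or add them to the comparison.

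**The concern.** The objective and the hypothesis describe different cost outcomes. The difference between them is the postpartum part of the delivery stay, which the protocol itself expects the intervention to shorten. Discharge happens after randomisation and is expected to move with the arm, so the starting point of the cost window is itself affected by treatment. A day of care avoided before discharge earns no credit, while a visit that replaces it after discharge is charged. The primary cost result therefore need not equal the eight-week effect that the objective asks for.

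The length-of-stay point is smaller but similar in kind: the hypotheses concern medians, and the only named tests for continuous data compare means. If the named tests are simply applied, the report could claim or deny a median reduction on evidence about something else.

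**Working it through.** The plan has no figure to reproduce here. It gives no mean, SD or share for any cost or length of stay, and the sample size (about 1000 per arm) is a recruitment forecast not tied to these outcomes. The ratios and distributions below are assumptions, used to show what follows from the definitions.

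**1. What each window measures.** Let Δstay be the between-arm difference in mean cost of the delivery stay after birth, and Δpost the difference after discharge.
- Objective (delivery to week eight): Δstay + Δpost.
- Hypothesis (discharge to week eight): Δpost only.
- Gap: Δstay. It is zero only if remote monitoring does not change delivery-stay cost, which is contrary to the protocol's rationale.

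**2. Possible size of the gap.** Set the usual-care post-discharge mean to 1, let post-discharge cost fall by 0.50 (the hypothesised threshold), and let the stay saving be s. The share of the total saving captured from discharge onward is 0.50/(0.50 + s):
- s = 0.5: 0.50/1.00 = 50%
- s = 1: 0.50/1.50 = 33%
- s = 2: 0.50/2.50 = 20%

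**3. Window length alone.** Eight weeks is 56 days. With an assumed 3-day stay the window is 53 days, and discharge one day earlier makes it 54: 54/53 − 1 = 1.9%. Stays of 2 or 4 days also give about 1.9%. The extra day of exposure is minor. What matters is which costs fall on each side of discharge.

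**4. Effect on the percentage.** With delivery-stay cost included, the overall percentage reduction is the average of the stay and post-discharge reductions, weighted by usual-care cost. If post-discharge cost falls by exactly 50%, the overall figure is below 50% whenever stay cost falls by less than half.

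**5. Mean test against median hypothesis.** Assumed distributions over stays of 1, 2, 3, 4, 5 and 10 days; Welch t-test, 1000 per arm, 3000 simulated trials, 5% level.
- Example A: usual care 10, 50, 25, 10, 3, 2%; remote monitoring 20, 55, 18, 5, 1.5, 0.5%. Both medians are 2 days; means are 2.60 and 2.165. The t-test rejects in 100% of runs with no change in the median.
- Example B: usual care 5, 40, 45, 7, 3, 0%; remote monitoring 10, 49, 30, 4.5, 1.5, 5%. The median falls from 3 to 2 days, while the mean rises from 2.63 to 2.735. The t-test rejects in 38% of runs, and the mean difference points the opposite way to the median.

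Power is not the difficulty: a 1-day mean difference needs 9 to 142 per arm for 80% power with SDs from 0.75 to 3 days (assumed). The target quantity is.

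**6. Programme cost.** If c is programme cost per woman as a fraction of the usual-care post-discharge mean, a 50% reduction nets 0.50 − c: +0.40 at c = 0.10, zero at c = 0.50 and −0.25 at c = 0.75. The documents give no value for c.

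**The case against.** Several points on the other side are sound.

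- **The hypothesis may be the working definition of a loosely worded objective.** That is possible, but the document does not say so, and the two readings give different outcomes.
- **The delivery-stay effect is not lost.** Length of stay is collected and has its own hypothesis. This stands: only the cost of the stay is missed.
- **The omission may be conservative.** If the stay shortens as expected, leaving out its cost, taken alone, understates the saving. This also stands. A reader might infer that the cost result is inflated or would change sign, but the documents contain no cost figures that show either.
- **The t-test is optional.** The Analytical Plan says such tests may be used and allows others. The fault is that no median analysis is specified; none is ruled out. Nor is a mean comparison wrong for cost, since the hypothesis is about the average: "We hypothesize >50% average total cost reduction (charges and amount paid, examined separately".
- **No net saving is claimed.** The objective is cost to the patient, for whom the cuff and app are free. A reader might infer that programme resources go unbilled or were deliberately excluded, but the documents are silent on both. The omission matters only for the use of the results: the Background says cost evidence is needed to establish sustainability, and the Secondary Objective lists sustainability planning.
- **Stay before randomisation.** Women enrolled after delivery have already used part of their stay. A reader might call this bias, but randomisation balances it in expectation. It adds noise.

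It is also tempting to call the >50% target unattainable because only about 2% of women are readmitted for hypertensive disorders. The documents give no breakdown of post-discharge cost, and they also hypothesise shorter readmissions and less acute-care use, so that conclusion is not supported.

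**Conclusion.** The concern holds in two parts. First, the cost window in the hypothesis contradicts the objective and the outcome list. As written, it leaves out the delivery-stay cost effect that the protocol gives as part of its rationale. The gap equals the between-arm difference in delivery-stay cost. Its size cannot be fixed from the documents; the 50%, 33% and 20% capture figures rest on assumed ratios and on a post-discharge reduction of exactly 50%. Second, and less serious, the median length-of-stay hypotheses have no matching analysis, and a comparison of means neither establishes nor refutes a difference in medians.

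Neither part undermines the randomised comparison. Both should be settled in the plan before outcome data are analysed. The programme-cost point is a limit on interpretation: the planned result is gross of programme cost and cannot by itself support a statement about net saving.

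**What to change.** - **Cost window.** Reconcile the Health care costs section with the Primary Objective and Outcome Measures. Measure cost in both arms from delivery through eight weeks postpartum, or from the start of the delivery admission if the bill cannot be split at delivery.
- **Cost reporting.** For charges and amount paid separately, report the delivery-stay component, the post-discharge component and their total. Give the difference in mean cost with a bootstrap confidence interval.
- **Length of stay.** Name a difference in medians with a confidence interval, by quantile regression or bootstrap, as the analysis for both median hypotheses.
- **Interpretation.** If the cost result is used to argue sustainability, state that it is gross of programme costs.

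The cost of the change is mainly wording, since billing linkage and length-of-stay data are already planned. The documents do not say whether the delivery bill can be split at delivery, hence the fallback. The delivery stay will add variance, and the percentage reduction on the larger base may be smaller than the hypothesised >50%. Keeping the post-discharge component as a separate line preserves the quantity now hypothesised.

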## **Analytical Plan**

The subject will complete a baseline demographic questionnaire at the time of enrollment. This questionnaire will be completed electronically through a unique link via REDCap. Additionally, subjects in the rBPM study arm will be asked to complete a post-study questionnaire electronically through a unique link via REDCap ~ 1 week after subject has completed the study.

The following EHR-based clinical measures will be obtained from each subject:

- Demographics
- History of hypertension or use of blood pressure lowering agents
- Pregnancy-related data (e.g. blood pressure, pre-pregnancy BMI, weight gain, complications, pre-pregnancy diabetes, gestational diabetes, delivery complications)
- Birth outcomes, including gestational age at delivery, cesarean or vaginal delivery, singleton or multiparous delivery, birth weight
- Length of stay of admission and any readmissions through 12 weeks postpartum
- Use of blood pressure lowering agents through 12 weeks postpartum

We will link EHR, BP, baseline demographic questionnaire data, billing, and user satisfaction data to inform study questions as described above. Data will be reviewed for missingness, with multiple imputation performed as appropriate. Initially, data will be analyzed using descriptive statistics. Comparison between groups may be performed using chi square tests for proportions, and t-tests or ANOVA procedures for continuous variables. Crude and adjusted regression analysis will be performed to identify independent outcome predictors. Other inferential statistical analysis will be conducted as appropriate.

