### **Sample Size**

It is estimated that approximately 5,000 women will deliver in Forsyth County over a 30 month time period. Of these, we anticipate that approximately 2000 women will be randomized equally (1000 in each study arm) during this time period.

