### **Interventions and Interactions**

After obtaining informed consent electronically via REDCap, all subjects will be asked to complete a questionnaire using REDCap in order to collect baseline demographic data. Collecting this demographic data directly from the subject is to ensure accuracy. It has been reported that race, ethnicity, and even preferred language data may be missing from a subject's EMR or may have been previously entered into the EMR incorrectly (internal report). Additionally, collecting data on the subject's education level and marital status may help inform health disparities among various subject groups.

The subject will be directed to the demographic questionnaire after signing the electronic consent form via REDCap. The questionnaire must be completed in order to randomize the subject to a study arm. It is estimated that it will take  $\leq 5$  minutes to complete the baseline questionnaire. The baseline questionnaire will be available in both English and Spanish.

The subjects randomized to the rBPM study arm will receive a specialized Bluetooth enabled BP cuff/monitor from a NEST Coordinator in the hospital after delivery and before they are discharged home. The subject will receive both verbal and written education (in the subject's primary language) on the correct use of the specialized BP cuff/monitor. (*Appendix 7a and 7b*). The BabyScripts app will be downloaded on the subject's personal smartphone utilizing either an iOS or Android operating system. Instructions on the use of the BabyScripts app will be provided verbally and in writing (in the subject's primary language). The data entered into the BabyScripts app by the subject includes the following: name, email, DOB, cell phone number, pre-pregnancy weight, height, and date of (actual or expected) hospital discharge following delivery. The subject's pre-pregnancy weight and height are utilized by the app to calculate the subject's BMI, which will then help to identify the correct size of BP cuff that the

subject should be using for this study. Using an oversized or undersized BP cuff can result in erroneous BP measurements. The BabyScripts app is downloaded at no cost to the subject. Per the Master Agreement with BabyScripts, BabyScripts does not sell or share any personal data collected through the app.

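### The plan commits to no baseline-adjusted arm effect: the group comparisons it names are unadjusted, and adjusted regression is aimed at finding predictors

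*Combined protocol and SAP*

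**What the plan says.** The Analytical Plan section is the whole statistical plan. On comparing groups it says: "Comparison between groups may be performed using chi square tests for proportions, and t-tests or ANOVA procedures for continuous variables". These methods use no covariates, and the wording is permissive. On regression it is firmer, but with another purpose: "Crude and adjusted regression analysis will be performed to identify independent outcome predictors". It closes with an open clause: "Other inferential statistical analysis will be conducted as appropriate". No section gives a treatment-effect model, a covariate list or a model for each outcome.

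Baseline data are available. Under Interventions and Interactions, the demographic questionnaire is a condition of entry: "The questionnaire must be completed in order to randomize the subject to a study arm". The EHR measures in the Analytical Plan include "History of hypertension or use of blood pressure lowering agents", and also pregnancy blood pressure, pre-pregnancy BMI and diabetes. The same list holds items that arise later, such as stay, readmission and "Use of blood pressure lowering agents through 12 weeks postpartum". Allocation is 1:1, and Methods and Measures describes no stratification.

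**The concern.** Cost is a primary outcome, and length of stay and readmission are secondary ones. Cost and stay are likely to vary widely between women for reasons present before randomization, such as hypertension or high BMI. An unadjusted comparison leaves that variation in the error term and gives wider intervals than the data allow. With no stratification described, chance imbalance on these factors also goes uncorrected, and this matters most in the smaller subset with hypertensive disorders of pregnancy (HDP).

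The wording also leaves open, until the data are seen, whether a crude or an adjusted arm effect is reported and which covariates enter. A model built to find predictors need not separate variables fixed before randomization from those that the arm can change.

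**Working it through.** **The plan's own figure.** Sample Size states: "Of these, we anticipate that approximately 2000 women will be randomized equally (1000 in each study arm) during this time period". This is an accrual estimate with no alpha, power or test behind it, so there is no calculation to reproduce. Assumed below: 1000 per arm, two-sided alpha 0.05, no dropout.

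**Continuous outcomes (cost, stay).** If baseline covariates explain a fraction R² of the outcome variance, linear adjustment multiplies the standard error of a mean difference by √(1 − R²). The equivalent sample size is multiplied by 1/(1 − R²). The smallest difference detectable with 80% power, in SD units, is (1.960 + 0.842) × √(2/1000) × √(1 − R²). R² is not in the documents; the range is assumed.

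| R² | SE ratio | SE reduction | Equivalent total N | Detectable difference (SD) | Power where unadjusted power is 80% |
|---|---|---|---|---|---|
| 0 | 1.000 | none | 2000 | 0.125 | 80% |
| 0.1 | 0.949 | 5% | 2222 (+11%) | 0.119 | 84% |
| 0.2 | 0.894 | 11% | 2500 (+25%) | 0.112 | 88% |
| 0.3 | 0.837 | 16% | 2857 (+43%) | 0.105 | 92% |

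The formula is for means. The stay hypothesis under Clinical outcomes is worded as a median difference, so for stay the table is only a guide.

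**Readmission.** The control rate is about 2%. The hypothesised absolute decrease of 60% cannot be taken from 2%, so it is read here as relative: 2% to 0.8% (assumption).

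- Unadjusted SE = √[(0.02 × 0.98 + 0.008 × 0.992)/1000] = 0.00525.
- Power = Φ(0.012/0.00525 − 1.96) = 63%.
- With the SE multiplied by √(1 − R²), power is 65% at R² = 0.05, 67% at 0.1 and 72% at 0.2.

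**Blood-pressure ascertainment primaries.**

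- 30% vs 90% in all women: power is about 100% with 1000 per arm. The 95% half-width goes from 3.4 to 3.2 percentage points at R² = 0.1.
- 60% vs 90% in HDP women: power is 94.6% with 50 per arm and 99.9% with 100 per arm (HDP share of 5% or 10%, assumed).

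**Which covariates are baseline values.** Methods and Measures allows enrolment at a clinic visit from 24 weeks. For these women randomization can precede delivery, and the arm is documented in the EMR. HDP diagnosed after that point, and delivery complications, are therefore not baseline values for them. Within the HDP-only analysis, HDP status is close to constant and adds little as a covariate. Insurance status, enrolment route and clinic are not itemised in the Analytical Plan list, although the insurance hypotheses need the first.

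**The case against.** The strongest reply has four parts.

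1. **The text excludes nothing.** The simple tests are only permitted, regression is what will be done, arm could enter it as a predictor, and the closing clause is open. A reader might infer that the plan rules out an adjusted arm effect. The documents do not support that. They also do not commit to one, and that is the point.
2. **Unadjusted tests are sound.** Under 1:1 randomization they are valid, so omitting covariates is not an error. This stands.
3. **The hypothesised effects do not depend on adjustment.** With 0.125 SD detectable, a one-day difference in mean stay has 80% power unless the SD exceeds 1/0.125 = 8 days. A halving of mean cost has it unless the SD exceeds 0.5/0.125 = 4 times the control mean (common SD assumed). Adjustment does not rescue readmission, and the feasibility primaries concern one arm only. This also stands, but those effects are hypotheses, and a narrower interval is most useful if the true effects are smaller.
4. **No mediator adjustment is proposed.** A reader might infer that the plan will adjust the arm effect for stay or postpartum drug use and so bias it. The EHR list is a list of data to collect, not of covariates, and stay and readmission are on it as outcomes. The bias would arise only if an unspecified adjusted model with such terms were used to report the arm effect.

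**Conclusion.** The point holds as a low-cost improvement, not as a flaw in validity. The plan collects prognostic baseline data and does not commit to using them in the arm comparison.

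For cost and stay, an assumed R² of 0.1-0.3 gives standard errors 5-16% smaller. The readmission gain is modest (63% to about 67% power at R² = 0.1, under the relative reading), and the gain for the ascertainment primaries is small. If baseline covariates predict little, the benefit shrinks accordingly. A claim that the planned tests are biased or that the primaries are underpowered for want of adjustment would go beyond the documents.

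**What to change.** In the Analytical Plan, state for each two-arm outcome that the main comparison is a regression on arm plus a fixed covariate set known at randomization:

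- history of hypertension, including HDP diagnosed before randomization;
- pre-pregnancy BMI;
- insurance status;
- enrolment route (prenatal or postpartum);
- clinic, if recorded.

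Confirm that insurance, route and clinic are in the linked dataset. For binary outcomes, report standardised absolute risk differences, which keep the absolute-difference target under Clinical outcomes. For cost and stay, report adjusted mean differences with robust standard errors.

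State that variables able to arise after randomization are not covariates in the arm-effect model: HDP diagnosed after randomization, delivery complications, length of stay, postpartum blood-pressure-lowering agents and readmission. Keep the chi-square and t-tests as the unadjusted check, and keep the predictor regression as a separate analysis.

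The cost is analysis text, slightly more analysis work and the dataset check. No visit, procedure or element of care changes.
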